In a pilot study 18 overweight/obese subjects with heart failure (all exceeded 40% body fat) were studied. Nine subjects received 12 weeks of dietary supplementation with 20 g of whey protein consumed daily, while the other nine were controls. Consistent with the acute data showing a limited stimulation of muscle protein synthesis with dietary amino acids in the profile of whey protein in even healthy elderly (i.e., anabolic resistance, Figure 1), supplementation with whey protein failed to improve functional performance. The lack of a demonstrable effect of whey is consistent with the diminished responsiveness to the stimulation of muscle protein synthesis by whey protein in heart failure (10). In contrast, a 2016 UAMS pilot study found that the EAA mixture is better at overcoming anabolic resistance than Ensure Heart Health (see below).

[figure not shown]

Figure 5. Average rates of Protein synthesis, breakdown and net balance between synthesis and breakdown after consumption of Ensure Heart or UpBeat. **significantly different from fasted state ($p < 0.005$); ***significantly different from fasted state ($p < 0.0005$); ## significantly different between treatments ($p < 0.005$).

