2.0 Hypotheses

1. We propose that 12 weeks of regular consumption of EAA mixture will improve physical function in individuals with heart failure as compared to placebo.
2. We propose that regular consumption of EAA mixture will improve health-related quality of life as compared to placebo.

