3.6 Study Products

The active study product is 9g twice a day of EAA mixture, a proprietary formula of Essential Blends, LLC (Fairbanks, AK). Product is a blend of amino acids, flavorings, caffeine and sweeteners (see Appendix) in powder form; packaged in 200g sealed containers. Subjects will dissolve 1 scoop of supplement into ~7 ounces of water and stir/shake until fully dissolved. They will be provided with shaker cups free of charge. Servings will be ingested between meals so that they ingest 2 servings per day. EAA mixture is currently available in only one flavor (lemon/lime).

The placebo product is 9g twice a day of Pure Protein 100% Whey protein (Worldwide Sport Nutritional Supplements, Inc., Bayport, NY). Unblinded study staff will repackage this product into 200g sealed containers which contain the appropriate scoops. See appendix for product information. Subjects will dissolve 1 scoop of supplement into ~7 ounces of water and stir/shake until fully dissolved. Servings will be ingested between meals so that they ingest 2 servings per day.

Subjects will be asked to save empty containers and return them to the study site for accountability purposes. Storage of both products is in a dry area at room temperature. Containers will be labelled identically, with the only difference being the study product code (A or B); the key to which is known only to the unblinded study staff until blinding has been broken at the end of data analysis.

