7.4 EAA mixture or placebo Effect

The following power calculations are based on a two-sample t-test which is being used as an approximation of the ANCOVA model. With 30 subjects in each EAA mixture and placebo group and an α -level of 2.5%, a two-sample t-test will have approximately 80% power to detect effect sizes of 0.82 standard deviation units or larger. **Table 4** presents the hypothesized group means for each endpoint as well as the corresponding EAA mixture or placebo effect and power estimate. These estimates correspond to approximately 25% (6-minute walk) to 50% (gait speed) of the differences in the values between individuals with heart failure vs age-matched healthy controls as determined in our Phase I protocol. Our previous outcome studies with EAAs indicate that these levels of improvement are expected (e.g., 11, 12, 13).

Table 4. Hypothesized group means and within group standard deviation used to estimate the power of the nutritional therapy effect when N=60 (30 per group) are enrolled. The calculations assume that an α -level of 2.5% will be used to determine statistical significance.

Endpoint	Hypothesized Mean Changes [#]		σ_{Δ} ^{\$}	Effect Size	Power (%)
	Control	Nutritional product			
6 Minute Walk ^a	0	105.1	89.3	1.18	98.67
Leg Strength ^a	0	11.0	13.3	0.83	81.31
Grip Strength ^a	0	4.1	4.6	0.89	87.19
10m Gait Speed ^a	0	0.23	0.28	0.82	80.80

#Means of the baseline and post-treatment changes for each group.

§Estimated within group standard deviation of the changes.

^aEstimates of σ_{Δ} were obtained from pilot studies performed at the UAMS Pepper Center.

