11.0 Appendices

11.1 Study Product Information

EAA mixture

His	3.5%
Ile	7.1%
Leu	14.3%
Lys	6.0%
Met	3.3%
Phe	8.8%
Thr	5.3%
Trp	1.4%
Val	9.25%
Glutamine	1.2%
Carnitine	2.9%
Nicotinamide	1.5%
Vitamin C	1.5%
Caffeine	0.6%
Sucralose and other flavorings and preservatives	28.3%

Placebo: Pure Protein – Vanilla Creme flavor

Directions: For adults, take one (1) scoop (39 g), one to two times daily. For maximum muscle support consume 1-2 scoops twice per day, with at least 1-2 scoops taken immediately after exercise.

Nutrition Facts

Serving Size 1 Scoop (39g)
Servings Per Container about 23

Amount Per Serving		
Calories 150		Calories from Fat 25
		%Daily Value*
Total Fat 2.5g		4%
Saturated Fat 1g		5%
Trans Fat 0g		
Cholesterol 80mg		27%
Sodium 100mg		4%
Potassium 160mg		5%
Total Carbohydrate 8g		3%
Dietary Fiber 0g		0%
Sugars 2g		
Protein 25g		50%
Vitamin A 0%		Vitamin C 0%
Calcium 20%		Iron 0%
Phosphorus 10%		Magnesium 4%

*Percent Daily Values are based on a 2,000 calorie diet. Your daily values may be higher or lower depending on your calorie needs:

	Calories:	2,000	2,500
Total Fat	Less than	65g	80g
Sat Fat	Less than	20g	25g
Cholesterol	Less than	300mg	300mg
Sodium	Less than	2,400mg	2,400mg
Potassium		3,500mg	3,500mg
Total Carbohydrate		300g	375g
Dietary Fiber		25g	30g
Protein		50g	65g

Calories per gram:
Fat 9 • Carbohydrate 4 • Protein 4

INGREDIENTS: Protein Blend (Ultrafiltered Whey Protein Concentrate [which contains Beta-lactoglobulin, Alpha-lactalbumin and Glycomacropeptides], Microfiltered Whey Protein Isolate), Maltodextrin, Natural and Artificial Flavors, Cellulose Gum, Soy Lecithin, Xanthan Gum, Dicalcium Phosphate, Calcium Carbonate, Acesulfame Potassium, Sucralose.

Contains milk and soy ingredients.

Typical Amino Acid Profile (milligrams per 39 g scoop**)			
Essential Amino Acids		Nonessential Amino Acids	
Histidine	490 mg	Alanine	1,139 mg
Isoleucine	1,460 mg	Arginine	640 mg
Leucine	2,531 mg	Aspartic Acid	2,980 mg
Lysine	2,127 mg	Cysteine	601 mg
Methionine	562 mg	Glutamic Acid	3,919 mg
Phenylalanine	808 mg	Glycine	444 mg
Threonine	1,783 mg	Proline	1,415 mg
Tryptophan***	485 mg	Serine	1,299 mg
Valine	1,376 mg	Tyrosine	728 mg

***L-tryptophan is naturally occurring, not added.
**approximate values

©2014 Carefully Manufactured by
Worldwide Sport Nutritional Supplements, Inc.
Bayport, NY 11705

For questions or reorders call:
[name]
or visit our website at
www.pureprotein.com

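### The control called placebo is whey protein with about half the essential amino acids of the active arm, so the trial tests EAA mixture against whey; the hypotheses should say so, and Table 4's zero control change needs a basis

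*Combined protocol and SAP*

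**What the plan says.** Section 3.6 defines the two arms by equal mass of powder. For the active arm: "The active study product is 9g twice a day of EAA mixture, a proprietary formula of Essential Blends, LLC (Fairbanks, AK". For the control: "The placebo product is 9g twice a day of Pure Protein 100% Whey protein".

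Section 2.0 states both hypotheses against placebo. The first is that the mixture "will improve physical function in individuals with heart failure as compared to placebo"; the second is that "regular consumption of EAA mixture will improve health-related quality of life as compared to placebo". Section 7 uses the same label for the control throughout the model description.

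Table 4 in Section 7.4 ("Hypothesized group means and within group standard deviation used to estimate the power of the nutritional therapy effect") enters a control change of 0 for all four endpoints. Its footnote gives a source for the standard deviations. Neither the footnote nor the text of Section 7.4 gives a source for the zeros.

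Section 1.0 describes a pilot in heart failure with nine subjects on 20 g of whey protein daily for 12 weeks and nine controls, and reports that "supplementation with whey protein failed to improve functional performance". It gives no means, standard deviations or intervals. Appendix 11.1 prints the composition of both products, including the whey label's "Typical Amino Acid Profile (milligrams per 39 g scoop").

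**The concern.** A reader of Sections 2.0 and 7 alone would take the treatment effect to be EAA mixture against no active supplement. The control is in fact a source of the same nutrients that make up most of the active product. The protocol does not treat such products as irrelevant: Section 4.2 excludes people who will not give up non-study protein or amino acid supplements.

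Two things are at stake. The first is interpretation. If the arms do not differ, the placebo label invites the conclusion that the mixture does nothing, although both arms may have improved. The second is power. Any gain in the whey arm comes straight off the between-group difference on which Table 4 relies.

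**Working it through.** **1. Essential amino acids per day.** Inputs are the Appendix 11.1 percentages for the EAA mixture (taken as percentages by weight), the whey label amounts per 39 g scoop (marked there as approximate), and 2 × 9 g = 18 g of powder a day in each arm (Section 3.6).

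Active = percentage × 18,000 mg. Whey = label mg × 18/39.

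| Amino acid | Active, mg/day | Whey, mg/day | Whey/active |
|---|---|---|---|
| Histidine | 630 | 226 | 36% |
| Isoleucine | 1,278 | 674 | 53% |
| Leucine | 2,574 | 1,168 | 45% |
| Lysine | 1,080 | 982 | 91% |
| Methionine | 594 | 259 | 44% |
| Phenylalanine | 1,584 | 373 | 24% |
| Threonine | 954 | 823 | 86% |
| Tryptophan | 252 | 224 | 89% |
| Valine | 1,665 | 635 | 38% |
| **Total** | **10,611** | **5,364** | **51%** |

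Check on totals: 58.95% × 18 g = 10.61 g; 11.622 g × 18/39 = 5.36 g; 5.36/10.61 = 0.506. Whey protein is 25/39 × 18 = 11.5 g a day.

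**2. Reproducing Table 4.** Two-sample t-test, 30 per arm, two-sided α = 2.5%, 58 degrees of freedom, critical value 2.301. The non-centrality is (product change − control change)/SD × √(30/2).

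| Endpoint | Change/SD | Non-centrality | Power, recomputed | Power, Table 4 |
|---|---|---|---|---|
| 6-minute walk | 105.1/89.3 = 1.177 | 4.558 | 98.67% | 98.67% |
| Leg strength | 11.0/13.3 = 0.827 | 3.203 | 81.38% | 81.31% |
| Grip strength | 4.1/4.6 = 0.891 | 3.452 | 87.19% | 87.19% |
| Gait speed | 0.23/0.28 = 0.821 | 3.181 | 80.80% | 80.80% |

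Table 4 is therefore correct arithmetic, given a control change of zero.

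**3. Margin around the zero.** Power of 80% with 30 per arm needs an effect size of 0.814. The largest control change that keeps 80% power is product change − 0.814 × SD (0.81376 unrounded), in the units of Table 4.

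| Endpoint | Largest control change | Share of hypothesised gain |
|---|---|---|
| 6-minute walk | 105.1 − 72.67 = 32.4 | 31% |
| Leg strength | 11.0 − 10.823 = 0.18 | 1.6% |
| Grip strength | 4.1 − 3.743 = 0.36 | 8.7% |
| Gait speed | 0.23 − 0.2279 = 0.002 | 0.9% |

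**4. Illustrative non-zero control changes.** The 10% and 25% shares are assumptions; the documents give no such figure. Effect size = Table 4 effect size × (1 − share).

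| Control gain, as share of hypothesised gain | Walk | Leg | Grip | Gait |
|---|---|---|---|---|
| 0% | 98.7% | 81.4% | 87.2% | 80.8% |
| 10% | 96.2% | 71.9% | 78.8% | 71.2% |
| 25% | 86.5% | 54.3% | 61.5% | 53.7% |

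**5. What a pilot of nine per group can show.** With 16 degrees of freedom, the 95% interval for a difference has half-width 2.120 × √(2/9) = 1.00 SD. Power for a true effect of 0.82 SD at two-sided 5% is about 37%. A finding of no improvement at that size is compatible with effects as large as three of the four in Table 4.

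**The case against.** There is a good case for the plan. The comparator is not hidden: Section 3.6 names it, Section 5.4 lists its allergens, Appendix 11.1 prints its label, and Table 4 heads the column as control. The arms supply similar amounts of amino acid material (11.5 g whey protein against (58.95% + 1.2% glutamine) × 18 g = 10.8 g amino acids), which is a defensible control for testing composition. All of this stands, and it is why neither product needs to change.

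Some readers might infer that the trial cannot support any useful conclusion because its placebo is active. The documents do not bear that out. The randomised comparison with whey is valid, and if whey is neutral or mildly helpful, superiority over it is conservative relative to an inert control.

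A reader might also call the zero control change unsupported. That goes too far. Section 1.0 gives an anabolic-resistance rationale and a heart-failure pilot at 20 g of whey protein a day, more than the 11.5 g here. The support is still weak: nine per group, no figures, no link to Table 4. The pilot subjects were all overweight or obese with more than 40% body fat, whereas Section 4.1 admits BMI 18 to 45.

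Finally, it is tempting to assume that whey delivers half the benefit because it delivers half the essential amino acids. Nothing in the documents makes that share a proxy for benefit. Section 1.0 argues that the whey profile is poorly effective in these patients, and the active product also contains carnitine, nicotinamide and caffeine. No such scenario is used here.

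**Conclusion.** The concern holds as a matter of naming, interpretation and sensitivity. The trial estimates EAA mixture versus whey, with the control supplying 51% of the active arm's essential amino acids overall (24% to 91% by individual amino acid). A positive result would show superiority over whey; a null result would leave open whether neither arm or both arms improved.

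Table 4 contains no arithmetic error. Its zero control change is weakly supported and not cited, and for leg strength, grip strength and gait speed the slack is only about 2%, 9% and 1% of the hypothesised gain before power drops below 80%. The 6-minute walk has ample slack, about 31%.

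The composition figures rest on approximate label values and on reading the EAA percentages as by weight. The margins rest on Table 4's own means and standard deviations and do not depend on the illustrative 10% and 25% shares.

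**What to change.** Keep both products and the randomisation as they are, and amend the text as follows.

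- Name the control a whey protein active comparator in Section 2.0, throughout Section 7 and in all reports.
- Restate both hypotheses as superiority of EAA mixture over whey protein.
- State in Section 7 that a null between-group result does not show absence of an EAA effect. Report within-arm changes from baseline descriptively only, since they are not randomised comparisons.
- In Section 7.4, cite the whey pilot as the basis for the zero control change and give its numerical results with intervals.
- Add Table 4 rows for small non-zero control changes, labelled as assumptions, such as the 10% and 25% rows above.

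The cost is a wording amendment and a few extra power rows, with no additional patients or procedures. The downside is that the stated claim becomes narrower and the displayed powers somewhat less favourable.

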Dispense study product and diary		x	x	x	x	x	x	x	x	x	x	x	x	
Return study product and diary			x	x	x	x	x	x	x	x	x	x	x	x

¹ For criteria-related testing.² Can be done on visit 1 or 2.³ Between visits, at home. Calls will be made to remind subjects of the time for collection.⁴ For protocol endpoints.

⁵ If subjects unable to provide at this visit, they can take home a collection kit to return at next visit.

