3.4 Randomization

We will use computer randomization to assign subjects to one of two possible treatment groups. The randomization procedure will be stratified by gender. A randomization procedure will be implemented using an Excel spreadsheet. As a participant is identified and enrolled on study, the study coordinator will ascertain gender, which will determine the next randomization.

A: subjects will consume 9g of EAA mixture supplement twice daily for 12 consecutive weeks.

B: subjects will consume 9g of placebo twice daily for 12 consecutive weeks.

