3.5 Blinding

This is a double-blinded study. EAA mixture will be provided by Prinova Inc. (Carol Stream, IL). Placebo will be purchased from online or local sources (Pure Protein website, Wal-Mart, etc.). Product containers will be coded so that only the unblinded study staff will know product

identity. After all study visits have been performed and all data entered into a database, the blind will be broken. Although the study products differ in taste, subjects will not be told which products are offered in which flavors.

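### Section 3.6 labels every container with one of two trial-wide codes, so one letter linked to one flavour decodes every label a person sees; a code per subject would stop that spread cheaply.

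*Combined protocol and SAP*

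**What the plan says.** Section 3.5 calls the study double-blinded and rests this on coding: "Product containers will be coded so that only the unblinded study staff will know product" identity. It then concedes the weak spot: "Although the study products differ in taste, subjects will not be told which products are offered in which flavors". That safeguard is directed at subjects and does not mention staff.

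Section 3.6 fixes the form of the code: "Containers will be labelled identically, with the only difference being the study product code (A or B". The key is to stay with the unblinded staff. The same section states that "EAA mixture is currently available in only one flavor (lemon/lime"), and Section 11.1 gives the placebo as "Vanilla Creme flavor".

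Section 3.4 uses the same two letters for the randomised groups: "A: subjects will consume 9g of EAA mixture supplement twice daily for 12 consecutive weeks" and "B: subjects will consume 9g of placebo twice daily for 12 consecutive weeks".

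Containers change hands often. In the Table of Events the row "Dispense study product and diary" is marked at Visits 2 to 13, and the matching return row at Visits 3 to 14. Section 3.2 has study staff weigh the returned containers at the weekly visits and write the mass on them. Section 3.1 places container return and the walk, strength, grip and SF-36 assessments in the same visit at Visits 8 and 14.

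**The concern.** A blind that rests on coded containers is only as strong as the code. Here the code has two values for two products, and each product has one distinct flavour that the protocol prints. The key can therefore be worked out without being handed over. One subject's remark about a lemon or vanilla drink, heard by someone who has read the protocol and sees that subject's container, identifies that letter and, by elimination, the other one.

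What is at stake is how far a single disclosure travels. The 6-minute walk, maximal voluntary contraction of the leg and hand grip all depend on effort, and so on how a tester instructs and encourages. A tester who can read the arm from the label may test the two arms differently without meaning to. With a shared code, one slip reaches every labelled container that person sees. With a code per subject, it stays with the subject who made the remark.

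**Working it through.** The plan states no figure on this point, so there is nothing to reproduce. The check is a count.

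**Inputs**
- Distinct codes: 2 (Section 3.6).
- Products: 2, with one flavour each (Sections 3.6 and 11.1).
- Subjects: up to 80 enrolled, 60 completers, 30 per group (Section 3.0).
- Dose and duration: 9 g twice daily for 12 weeks (Section 3.4).
- Container size: 200 g (Section 3.6).
- Dispensing visits: 2 to 13, which is 12 visits (Table of Events).

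**Labels decoded by one letter-flavour link**
- Two trial-wide codes: the linked letter gives one arm and elimination gives the other. The upper bound is 30 + 30 = 60 of 60 completers, or 80 of 80 enrolled. It is reached only by someone who sees every label.
- One code per subject: 1 of 60 (1.7%) or 1 of 80 (1.25%).
- Several codes per arm, with five as an illustration: 60 / (2 × 5) = 6 of 60, or 80 / (2 × 5) = 8 of 80. Elimination no longer works, because the other codes could belong to either arm.

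**Which visits matter**
- Visit 2: Section 3.1 describes dispensing after the baseline assessments, and the subject has not yet tasted the product. This is weak support.
- Visit 8: used containers are returned, outcomes are tested and more product is dispensed.
- Visit 14: used and any full containers are returned and final outcomes are tested.

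The exposure that counts is therefore at Visits 8 and 14.

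**What the label change cannot reach**

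A person who weighs used containers may recognise the product directly. The documents give no rate. As an assumption, if a handler recognises it for 25% or 50% of subjects, 0.25 × 60 = 15 or 0.50 × 60 = 30 completers are known whatever the code. Under two codes, one such recognition is enough to decode all 60. Unique codes still help, but the contrast is then 60 against 15 or 30, not 60 against 1.

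**Labels needed for a code per subject**
- By mass: 18 g/day × 84 days = 1,512 g, and 1,512 / 200 = 7.56, so at least 8 containers per subject. 8 × 60 = 480 and 8 × 80 = 640.
- By dispensing: 12 × 60 = 720 and 12 × 80 = 960.

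**The case against.** The root weakness is the taste difference, and recoding does not touch it. The people who see the most labels may be the same people who handle used containers, and they may recognise lemon/lime or vanilla creme unaided. Harm also needs a chain that the documents do not establish: a tester who is meant to be blind, sees labels, knows the flavours, hears a remark, remembers the letter and then tests differently. Sections 3.5 and 3.6 provide for unblinded staff. If they do all the dispensing and weighing, testers need never see a label.

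Much of this stands. It limits the benefit to stopping spread through the label, and it makes this an improvement to a design choice, not a demonstrated failure of blinding. It does not remove the point. Sections 3.1 and 3.2 say only study staff for dispensing and weighing, no passage separates container handling from testing, and keeping the key secure does not help when the key can be inferred.

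A reader might infer three stronger things that the documents do not support:
- **The protocol prints the key, because Section 3.4 lists A as EAA and B as placebo.** The documents do not say that container code A is group A. The weakness does not depend on the overlap.
- **The false-positive rate rises by a definite amount.** That would need the chance of a remark, the rate of direct recognition, and the size and direction of tester bias in each arm. None is given.
- **Sections 3.5 and 3.6 contradict each other on when the blind is broken.** One places it after data entry and the other at the end of data analysis. They can be read as compatible.

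**Conclusion.** The point holds as a cheap improvement. With two trial-wide codes and printed flavours, one letter-flavour link decodes every label a protocol reader sees, up to 60 of 60 completers (80 of 80 enrolled). A code per subject limits label-based disclosure to one subject.

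This rests on the Section 3.6 wording being the full labelling scheme (no subject-level or kit-level code is described anywhere) and on some person who is meant to be blind seeing labels, which the documents neither state nor exclude. It does not show that unblinding has happened or will happen, and no error rate can be attached to it. Nor would unique codes make the blind secure, because flavour remains a direct route to the product for the individual subject. Sample size, power and significance level are unaffected.

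**What to change.** **Section 3.6.** Replace the A-or-B product code with a random container code unique to each subject, unrelated to the letters in Section 3.4. The existing unblinded staff hold the list. If bulk packing must be kept, use several random codes per arm; with five per arm, one link decodes 6 of 60.

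**Section 7.1, with a cross-reference in Section 3.5.** Unique codes with a concealed key would leave the analyst unable to form groups for the ANCOVA. State that the unblinded staff supply a masked two-level group variable that appears on no label and does not use the Section 3.4 letters, and that product identity is revealed only after the analysis is complete. This also settles the timing of unblinding across Sections 3.5 and 3.6.

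**Cost.** Subject-specific labelling in place of bulk labelling: about 480 to 640 labels by mass, or 720 to 960 if one per dispensing. The unblinded staff already repackage the placebo, so the added work is mainly labelling and list-keeping. The change leaves the taste difference, flavour recognition by those handling used containers, and the randomisation procedure in Section 3.4 as they are.
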